**Adjunctive Nitrous Oxide during ED propofol sedation in adults,
a pilot study.**

NCT02410707

Version: 7/1/14

Investigator(s): [name], DO; [name], DO; [name]; [name], CCRC

Objectives

To describe the safety and efficacy of adjunctive nitrous oxide pre-propofol administration for analgesia and pre-procedure anxiolysis during ED procedural sedation and analgesia in adults.

Background

Specific Aims

To measure the rates of hypoxia and respiratory depression requiring a physician intervention in adult patients receiving 50% demand valve nitrous oxide pre-propofol administration during ED procedural sedation and analgesia. Secondary aims include patient, nursing, and physician post procedure satisfaction scores, Ramsay sedation scores, total propofol dose given, length of time spent using nitrous oxide, patient recall of procedure.

Significance

Procedural sedation is the use of sedative, analgesic, and/or dissociative agents to relieve anxiety and pain associated with diagnostic and therapeutic procedures. Propofol has become one of the most commonly used agents for ED procedural sedation.^{1,2} Propofol crosses the blood-brain barrier rapidly. The drug takes effect within approximately 40 seconds, and its

duration of action is approximately six minutes^{2,3} Multiple randomized trials and prospective observational studies have found propofol to be safe and effective for PSA in the emergency department^{3,4,5}. Propofol acts as a sedative and amnestic, but provides no analgesia.

A possible approach is pretreatment with short-acting opioids (eg, fentanyl). Unfortunately, the addition of opioids increases the likelihood of respiratory complications. As an example, fentanyl at a dose of 1.5 mcg/kg increases the risk of respiratory depression. In another study, patients given both alfentanil and propofol required stimulation to induce respiration more often than those given only propofol.⁷ Another alternative to pretreatment with short-acting opioids is to use sub-dissociative doses of ketamine (0.3 mg/kg). Ketamine appears to provide comparable analgesia with less risk of respiratory depression. However, there is no literature that has shown that there is a decreased risk of respiratory depression than with propofol.⁸

The optimal agent for analgesia before procedural sedation would have effect that is short acting, easy to administer, and with minimal risk to the patient. Nitrous oxide may fit this profile. In pediatric emergency departments, inhaled nitrous oxide was found to be the most common agent for procedural sedation and analgesia.⁸ There is a great deal of literature supporting the use of nitrous oxide in the pediatric population, and the safety and efficacy of its use as a single agent or in concert with a parenteral sedative and/or analgesic is excellent. However, there is a paucity of literature to support or refute the use of nitrous oxide in adults for ED procedural sedation and analgesia.

Nitrous oxide is a colorless gas that diffuses rapidly across the pulmonary alveoli providing analgesia and anxiolysis with minimal sedative effects, rapid induction, and emergence.⁹ Nitrous oxide is a weak sedative agent with the potential for significant analgesic

effects. Noncompetitive antagonist activity at the NMDA receptor along with activation of opioidergic receptors contributes to its anesthetic mechanism.¹⁰ In an RCT (ENIGMA 1) using anesthesia with and without nitrous oxide, there was a small increased risk of myocardial infarction in the nitrous oxide group.¹¹ However, there were patients getting general anesthesia for over two hours; our patients will be receiving 50/50 nitrous oxide for 5-10 minutes maximum, and there are no known cardiac side effects reported during short-term sedation in the literature.¹¹ There are rare adverse events, most often cited as case reports of chronic or acute toxicity causing myeloneuropathies and polyneuropathies.¹²⁻¹⁵

Nitrous oxide has been used in general anesthesia for over 2 centuries, but its use outside of the operating room began when Tunstall introduced the nitrous oxide/oxygen mixture as an analgesic agent during labor.¹⁶ Since this inception, the nitrous oxygen/oxygen mixture has been used readily in the fields of dentistry, gastrointestinal procedures, and children's procedural sedation. Nitrous oxide is often administered via continuous flow or on-demand at a concentration of 50-70%.

There is some early data describing a favorable adverse event profile with nitrous oxide as a single agent in adults. Hennequin et al. (2012) demonstrated support for the efficacy of nitrous oxide with no major adverse cardiorespiratory events. Although approximately 10% of participants received mild gastrointestinal and behavioral side effects (e.g. agitation). Greater than 90% of the study participants stated they would receive nitrous oxide again.¹⁷ In a large prospective trial, Babl et al. (2008) found there to be only 2 patients out of 655 who suffered serious adverse events (i.e., chest pain and oxygen desaturation). Both patients had been administered 70% nitrous oxide compared to the more conservative 50% concentration. Additionally, there was an increased incidence of minor adverse events (i.e., emesis and

agitation) with the higher concentration of nitrous oxide.¹⁸ Kariman et al. (2011) compared nitrous oxide versus parental fentanyl as an analgesic after long bone fracture and found similar pain scores and a more rapid decrease in the pain score in the nitrous oxide group when compared with the opiate group.¹⁹

Nitrous oxide has been shown to be a safe and effective agent for procedural sedation in children, including work that has combined opiates and benzodiazepines with nitrous oxide continuously. Burton et al. (1998) conducted a small, randomized controlled trial studying the effectiveness of nitrous oxide on anxiety scores in children during laceration repairs. They found a significant decrease in the group that used nitrous oxide compared to the placebo group.²⁰ This finding was further validated by Luhmann et al. (2001) with 50% continuous flow of nitrous oxide resulting in less distress and anxiety as well as increased patient satisfaction compared to midazolam or topical anesthetic agents²¹. The study also showed that the main adverse event associated with nitrous oxide was nausea and vomiting, whereas the midazolam group had significant ataxia and dizziness. There was no demonstrable advantage of the combination of midazolam and nitrous oxide in regard to patient satisfaction versus nitrous oxide alone, but there was an increase in adverse events when midazolam was included.²¹ A study performed by Evans et al. (1995) demonstrated that the pain and memory of the procedure between children receiving either nitrous oxide versus children receiving intramuscular meperidine in combination with promethazine for fracture reduction was similar, but there was increased satisfaction and decreased length of stay in the nitrous oxide group.²² Seith et al. (2012) demonstrated that the addition of intranasal fentanyl to nitrous oxide in children resulted in deeper levels of sedation when compared to nitrous oxide alone; however, there were no serious adverse events.²³

Nitrous oxide as an adjunct to propofol may be an ideal agent to decrease pre-procedure anxiety before deep sedation of adults in the ED. Nitrous oxide has some analgesic and anxiolytic qualities, with an excellent cardio-respiratory profile. The anxiety and pain surrounding procedural sedation is not limited to the procedure itself, but the elapsed time from the time the patient enters the ED to the time spent in preparation for the procedure can be significant and lead to increased anxiety. This may lead to increased time and difficulty in sedating a patient to an appropriate level for a procedure. These patients may require higher levels of propofol to appropriately sedate, which is associated with increased rates of adverse respiratory events.

We believe that pre procedure adjunctive nitrous oxide may provide a level of anxiolysis and analgesia before propofol is administered, leading to a smoother and more satisfactory sedation and procedure, with fewer adverse respiratory events and less overall propofol dose than propofol alone. Since this is a novel concept, we believe that a pilot study to evaluate the safety and efficacy of pre-procedure adjunctive 50/50 nitrous oxide administration with adult propofol administration is warranted.

Setting of the Research

Patients will be recruited from the Emergency Department of Einstein Medical Center Philadelphia. The Einstein Medical Center Philadelphia is an urban teaching hospital, level one trauma center with 500 beds and an annual ED census of 100,000 subjects.

Resources Available to Conduct this Research

The Einstein Medical Center Philadelphia ED sees approximately 300 patients a day, of which 5% are emergencies that require procedural sedation and analgesia, and thus will be available as potential subjects in this study. The Division of Clinical Research of the Department

of Emergency Medicine has extensive experience in both investigator led and pharmaceutical research. This will be the seventh trial we have conducted in our ED in procedural sedation and analgesia in the last 7 years, and each of these studies has recruited 100-200 patients. We have a research associate 7 days a week who will consent and enroll eligible patients. The division also has 2 full time coordinators and a full time division director, as well as biostatistician support. We have two well-equipped offices, one in the ED where the research associate is based and one in our department where our division director works. The lead investigator will lead 10% of their non-clinical time to this endeavor.

Study Design

This pilot study will be conducted in a prospective, non-randomized fashion using a convenience sample of 100 subjects undergoing sedation for ED procedures.

1. Recruitment Methods

The research associates as well as the health care team (both residents and attending physicians) will screen patients who may need procedural sedation in the ED and may qualify for the study. Research associates will use the Cerner/AeCIS System for screening, and they will be in charge of informed consent, enrollment, placement of the capnography monitor, as well as data collection. The health care team will be in charge of the procedural sedation and all other management.

2. Inclusion and Exclusion Criteria

- i. Inclusion criteria: All spontaneously breathing subjects, 18 years of age and older, with an American Society of Anesthesiologists (ASA) Physical Status Classification 1 or 2, who will be receiving sedation for an ED procedure.

Written informed consent will be obtained from all subjects.

- ii. Exclusion criteria: Subjects with underlying conditions that could affect ventilation, perfusion, or metabolism including intubated subjects, subjects with clinical signs of cardiopulmonary instability, major trauma, shock, sepsis, ASA class 3, 4, and 5. Also those unable to provide informed consent, nursing home residents, age less than 18 years, non English speaking, pregnant women, subjects under police custody, or physician discretion.

3. Study Endpoints

- i. Primary:

1. ETCO₂ measured q 20 milliseconds seconds
2. SpO₂ measured q 20 milliseconds seconds

- ii. Secondary Endpoints

1. A baseline reading of the vital signs (heart rate, respiratory rate, peripheral SaO₂ and ETCO₂)
2. Physician interventions (verbal or physical stimulation, airway repositioning, additional oxygen, positive pressure ventilation, endotracheal intubation)
3. Level of sedation (Ramsay Score)
4. Patient Demographics
5. Patient recall of procedure
6. Total propofol dose
7. Total elapsed time of nitrous oxide use
8. Patient and physician procedure satisfaction score

4. Procedures Involved in the Research

Initial medical assessment will be made in accordance with established clinical procedures, including the history, physical examination, and vital signs. If by clinical assessment the patient meets eligibility criteria, then they will be approached by a research associate for enrollment in the study. After informed consent is obtained and prior to starting the sedation, standard vital sign monitoring will be placed on the patient (electrocardiogram, non-invasive blood pressure monitoring, pulse oximetry, and capnography). Level of consciousness will be determined using the modified Ramsay scale, which will be assessed at baseline. The Capnostream 20 ETCO₂ monitor will be used as the primary device to measure ETCO₂, with a nasal cannula capable of delivering supplemental oxygen and measuring ETCO₂ (Oridion Medical, Needham, MA).

The SEDARA gas mixer system [Linde Gas North America LLC] will be used as our primary nitrous oxide delivery device. It will mix and deliver nitrous oxide and oxygen in a 1:1 ratio, at a fixed concentration of 50%/50%. It uses a patient driven demand valve system that is hand held. This device provides a consistent, fixed 50%/50% blend of nitrous oxide (N₂O) and oxygen (O₂), eliminates the need to titrate, and provides fixed concentrations for controlled and consistent dosing. The device comparator detects dosing imbalance to protect against hypoxic mixtures, it cannot deliver nitrous gas without concurrent oxygen, and the device has an anti-asphyxia valve override. The on demand valve requires patient inspiration to trigger dosing. This portable device scavenges exhaled waste gases for environmental safety, as well as a key mechanism that renders the system inoperable without it for security.

After informed consent, the patient will fill out a pre procedure questionnaire and a 100 mm VAS baseline pain scale. The patient will be given the mask for delivery of nitrous oxide, and instructed on its use. The research associate will mark the time the patient began using the device electronically on the capnostream 20. Once IV access is established, and the team and

patient are ready to begin the procedure, the nitrous oxide mask will be removed, and a 100% NRB mask delivering 15 liters a minute of supplemental oxygen will be placed on the patients face. The loading dose of propofol will then be administered immediately. All sedations in this trial will use propofol 1.0 mg/Kg initial dose, with 0.5 mg/Kg doses titrated to deep sedation. Once the patient is deeply sedated, the procedure will begin.

The subject's clinical data and sedation information (refer to data management) will be entered into a standardized data collection form. The data will be continuously recorded throughout the sedation and recovery periods. Study will end when the subjects recovers back to baseline mental status.

Vital signs will be flagged electronically when a physician intervenes for clinical respiratory depression. Respiratory depression will be defined as peripheral SaO₂ below 92%, ETCO₂ level above 50, a rise or decrease of 10% above or below baseline, the loss of the ETCO₂ waveform for more than 15 seconds. Level of consciousness will be determined using the modified Ramsay scale, which will be recorded at baseline and at the point of deepest sedation. Once the procedure is complete, and the patient is deemed back to their mental status baseline, they will fill out a post procedure satisfaction questionnaire, and a 100mm VAS scale. They will be asked about procedure recall. The physician will also fill out a post procedure questionnaire.

5. Data Management

A standardized data collection form will be used to collect clinical data and a USB drive to collect electronic vital sign data. Initial data gathered will include age, gender, weight, and baseline vital signs (BP, HR, RR, peripheral SpO₂, and ETCO₂). Other information collected will be the elapsed time of nitrous oxide use, start time (when protocol was given), time (when patient returns to baseline), elapsed time in seconds under sedation (from start time to end time),

medications administered, repeated doses and times for every administered medication, total dose of each medication administered, adverse events, and interventions aimed at correcting respiratory depression. Level of consciousness using the modified Ramsay scale will also be recorded at baseline and at set intervals during sedation.

The electronic monitoring data will be continuously recorded into the USB drive throughout the sedation and recovery periods. The Capnostream 20 ETCO₂ monitor (Oridian Medical, Needham, MA) is capable of sampling and recording ETCO₂ and pulse SaO₂ every 5 seconds. A patient identifier will be recorded to link the subject and the electronic monitoring data without compromising his/her confidentiality. At the completion of the sedation, all device data will be transmitted to a password-protected Excel/SPSS spreadsheet for analysis. The research associate is responsible for recollection and storage of the data. Only the primary investigators, the study coordinator, and the research associates will have access to such.

To assess these outcomes, we will download electronic data from each sedation into a Microsoft Excel database, checked and adjudicated any discrepancies with research associate notations, and generate a graph of the subject's sedation with the X-axis showing time and the Y-axis depicting ETCO₂, SpO₂, respiratory rate, and heart rate. Electronic time stamps noted propofol administration, procedure initiation and completion, adverse events, and physician interventions.

Before study blinding is broken, three investigators will evaluate each graph to code the presence or absence of cerebral hypoxia, peripheral hypoxia and respiratory depression. We will disqualify graphs if they had >35% data loss, unless all three evaluators agreed that there was unequivocal evidence of hypoxia (cerebral and or peripheral) and/or respiratory depression.

6. Withdrawal of Subjects

Participation is voluntary. Subjects may withdraw from this study at any time. If this is the case their data will be deleted. We will record the number of patients that withdraw. Subjects may be withdrawn without their consent if the electronic data cannot be recorded.

Statistical Plan

1. Sample Size Determination

As this is a pilot, prospective, observational trial, no power calculation will be used to measure a difference. In previous propofol studies, approximately 10-30% of patients develop hypoxia, and approximately 50% of patients meet criteria for respiratory depression. Thus, we believe enrolling 100 patients in this observational trial will allow for approximation of any correlations that are measured.

2. Statistical Methods

All clinical observations and demographic data will be summarized using medians with range or means with standard deviations as appropriate. Rate of detection of respiratory depression and hypoxia and timing of these events for each instrument (near-infrared spectroscopy, pulse oximetry, capnography) will be summarized descriptively. Associations among SaO₂, and ETCO₂ will be estimated using spearman's rank correlation coefficient, using within-cluster resampling algorithm. This will allow for estimation of the marginal correlation in the presence of clustered data. Correlations not involving repeated measures data will be estimated with Spearman's rank correlation coefficient. All analysis will be conducted using SPSS software (IBM, Armonk, NY).

Risks to Subjects

There are no risks to the subjects other than the normal risks associated with the standard procedural sedation and analgesia, which may vary depending on the agent used, but in general include hypoxia, respiratory depression, hypotension, etc.

Potential Benefits to Subjects

There is no direct benefit for the subject. There will be no reimbursement to subjects for their participation in the study.

Provisions to Protect the Privacy Interests of Subjects

All data will be de-identified. Data that is loaded into the computer will be password protected and only available to the research associates and the investigators. Patients will be approached at their bedside by trained associates that will establish a private environment to disclose the information about this study and recollect the data. There will be no undue pressure placed to participate. All questions about the study may be answered by the research associates and the investigators prior, during and after informed consent is given.

Provisions to Maintain the Confidentiality of Data

Each subject will be given an identification number in the monitors and database in order to de-identify data for analysis. Study data will be stored for a minimum of 3 years in a secure and password protected file only accessible to study staff. Hard copy of data collection form will be kept in the research office under lock and only accessible to study staff.

Medical Care and Compensation for Injury

This is an observational study. No injuries can be consequence from participating in it. The procedural sedation and analgesia carries some risk that does not go beyond the standard ED protocol.

Cost to Subjects

There will be no cost to the subjects from participating in the study. Aspects that are part of standard clinical care will be responsibility of the subjects and their insurance companies.

Consent Process

Formal written consent will be completed by the patient with a trained research associate, who has extensive experience in research recruitment and consent. The consent discussion will be hold at the patient's bed side, and will last until the patient understand what is being told. Patient can ask any question related to the study and can take the time they consider necessary to consent. No coercion or undue influence will be placed to participate.

The signed documents will be stored in the study binder inside the research office and a copy will be given to each subject for their files.

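### The risk and injury sections deny any risk beyond standard sedation although the protocol gives every subject nitrous oxide; the stated maximum duration is also not carried into the procedures

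*Combined protocol and SAP*

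**What the plan says.** **Risk and injury.** Risks to Subjects says "There are no risks to the subjects other than the normal risks associated with the standard procedural sedation and analgesia", and continues "which may vary depending on the agent used, but in general include hypoxia, respiratory depression, hypotension, etc". Medical Care and Compensation for Injury says "This is an observational study. No injuries can be consequence from participating in it", followed by "The procedural sedation and analgesia carries some risk that does not go beyond the standard ED protocol". The word *observational* is also used twice for the design in Sample Size Determination.

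**The intervention and its cited effects.** Under section 4 (Procedures Involved in the Research), each consented patient is handed a mask delivering a fixed 50%/50% nitrous oxide and oxygen mix before propofol. Significance calls the concept novel and says "there is a paucity of literature to support or refute the use of nitrous oxide in adults for ED procedural sedation and analgesia". It also cites mild gastrointestinal and behavioral effects, such as agitation, in about 10% of participants given nitrous oxide alone. Nausea and vomiting are cited as the main adverse event in a pediatric trial, and neuropathies as rare, from case reports.

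**Duration.** Significance sets aside a small excess of myocardial infarction in a randomized anesthesia trial by contrasting exposures: "However, there were patients getting general anesthesia for over two hours", whereas "our patients will be receiving 50/50 nitrous oxide for 5-10 minutes maximum". Section 4 ends mask use when a line is in place and both sides are prepared: "patient are ready to begin the procedure, the nitrous oxide mask will be removed". Sections 3 to 5 give no limit in minutes. They make elapsed nitrous oxide time a secondary endpoint and a recorded item.

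**The concern.** The main issue is the risk wording. A protocol that assigns a drug, and whose first objective is to describe that drug's safety, cannot also say that participation adds no risk and can cause no injury. An ethics board or safety reader who relies on those two sections would not learn from them that an agent has been added, or what it is known to do. The *observational* label points the same way, because it suggests that sedation proceeds as it would have without the study.

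The second issue is smaller. A maximum exposure is part of the safety argument, but the section that bedside staff follow does not repeat it. Staff could keep to section 4 exactly and still go past 10 minutes.

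**Working it through.** There is no power, alpha or sample-size figure to reproduce here. The check compares sections of the text, with some arithmetic for scale.

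**Step 1. Risk statements against the rest of the protocol.**

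| Risk and injury sections | Elsewhere in the protocol |
|---|---|
| Only the risks of standard sedation apply | Nitrous oxide is given to every subject (section 4); the concept is called novel and the adult ED literature sparse (Significance) |
| Named risks: hypoxia, respiratory depression, hypotension | Cited for the gas: nausea, vomiting, agitation; rare neuropathy (Significance) |
| Observational; no injury possible | Drug, concentration, device and propofol dosing are all set by protocol (section 4) |

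Nausea, vomiting and agitation appear in the right-hand column only. Neuropathy needs its context. Significance attributes it to chronic or acute toxicity, and two of the four cited titles (references 14 and 15) concern abuse, one of them at high dose. Its relevance to one brief 50% exposure is not shown. Significance also cites 2 serious events in 655 patients (2/655 = 0.3%), but both were at 70%, so they are not counted here.

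**Step 2. Scale of the unnamed mild effects.** Inputs: N = 100 (Study Design) and about 10% (Significance, single-agent use). No rate is given for brief use before propofol, so 2% to 10% is assumed. The lower end has no source in the documents.

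- Expected number = 100 × rate: 2 at 2%, 5 at 5%, 10 at 10%.
- Chance of at least one = 1 − (1 − rate)^100: 1 − 0.98^100 = 0.87 at 2%; 1 − 0.90^100 = 0.99997 at 10%.

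**Step 3. Does a longer mask time undo the cardiac contrast?** The comparator is anesthesia of more than 120 minutes, so each ratio is an upper bound. The overruns are assumed values.

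- 10/120 = 8.3%
- 15/120 = 12.5%
- 20/120 = 16.7%
- 30/120 = 25.0%

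The contrast in exposure remains at 30 minutes. These ratios compare durations and do not measure risk.

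**Step 4. What the recorded times could show.** The documents give no mask-time or set-up figures, so no overrun rate can be estimated. With 100 subjects, the exact (Clopper-Pearson) 95% interval for the share above 10 minutes would be:

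- 0/100: 0 to 3.6% (upper limit 1 − 0.025^(1/100) = 0.036)
- 5/100: 1.6% to 11.3%
- 10/100: 4.9% to 17.6%

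The counts are illustrative.

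**The case against.** **On risk.** Risks to Subjects does say that risks depend on the agent and ends its list openly. Adverse events are collected and time-stamped under section 5, so nausea or agitation can be recorded even though it is not named in advance. Only ASA class 1 or 2 subjects enroll. The statement on safety capture stands: this is a gap in wording, not in data collection. The hedges do not rescue the text, because they still assign all risk to standard sedation and nothing in the protocol says nitrous oxide is part of the standard ED protocol. The no-injury sentence carries no qualifier at all.

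**On duration.** Much of the case against stands. Section 4 is silent on time; it does not contradict Significance. Readiness is not the only way exposure can end: the valve is hand-held and needs an inspiration to deliver gas, the care team manages the sedation, and a subject may withdraw. None of these is a time limit. Attachment A (device guide) or B (data collection form) could contain one, and neither is shown.

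**Stronger readings that a reader might infer.** The documents do not support any of these:

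- *Subjects will exceed 10 minutes.* Significance says preparation can take a significant time, but gives no figure.
- *An overrun would expose subjects to the cardiac risk seen in the anesthesia trial.* Step 3 points the other way for modest overruns, and Significance also relies on the absence of reported cardiac effects in short-term sedation.
- *Subjects were misinformed at consent.* The consent pages are not in this copy, so nothing can be said about them.
- *The results are compromised.* The ETCO₂ and SpO₂ endpoints, their analysis and N do not depend on these sentences.

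**Conclusion.** The main point holds with high confidence. The no-risk and no-injury statements and the *observational* label are contradicted by the protocol's own intervention and citations. In size, it concerns mild effects in perhaps 2 to 10 of 100 subjects. That range rests on the assumption that the rate for brief use before propofol lies between 2% and the 10% cited for single-agent use.

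The secondary point holds with moderate confidence, subject to Attachments A and B. A stated maximum is not carried into the procedures. It shows an unenforced limit, not an overrun or added cardiac harm.

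Overall severity is minor. The wording bears on subject protection and not on the statistical content.

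**What to change.** **Risk and injury sections.**

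- Delete the claim of no risks other than standard ones, and the sentence that no injury can result.
- List nausea, vomiting and agitation as risks of nitrous oxide. Mention neuropathy only with its context: rare case reports of chronic or acute toxicity, some of them abuse.
- Replace *observational* with *single-arm interventional pilot* in Medical Care and Compensation for Injury, and at both places in Sample Size Determination. Changing only one section would create a new inconsistency.

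**Duration.** Choose one:

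- Restate the figure in Significance as an expected duration and drop *maximum*. This is the simpler option and leaves the intervention as it is.
- If a hard limit is intended, write it into section 4: mask removed at readiness or at 10 minutes of mask time, whichever comes first. Define mask time from first use to removal, since time spent inhaling on a demand valve would be ambiguous. If an attachment already sets a limit, cite it in section 4.

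In either case, report the share of subjects above 10 minutes, with its exact interval, from the elapsed time already recorded.

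**Cost.** The wording changes take a few sentences, and the report adds one proportion from existing data. A hard stop costs more. Propofol is meant to follow mask removal at once, and nitrous oxide wears off quickly. In a slow set-up the stop would leave a gap without its analgesia and anxiolysis, and would change the treatment those subjects receive before propofol. The investigators should accept that knowingly or take the first option. Endpoints, analysis plan and N stay as they are under both.
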